# **4 STUDY POPULATION**

### 4.1 Selection of Study Population

Only those patients will be included in the study that meet inclusion and exclusion criteria as outlined below.

#### 4.2 Inclusion Criteria

Patients who meet all of the following criteria will be considered for inclusion in the study:

- 1. Be willing and able to provide written informed consent for the trial.
- 2. Be  $\geq 18$  years of age on the day of signing the informed consent.
- 3. Have an Eastern Cooperative Oncology Group (ECOG) performance status of 0-2.
- 4. Have histologically or cytologically confirmed advanced or metastatic gastroesophageal adenocarcinoma amenable to intratumoral injection (i.e. at least 1 cm in size).
- 5. Tumor must be PD-L1 positive, as defined by a combined positive score (CPS).
- 6. Patient must have received at least 2 lines of systemic therapy for advanced disease
- 7. Have one or more measurable lesions based on RECIST v1.1.
- 8. Be willing to provide tissue; newly obtained biopsy specimens or formalin-fixed, paraffinembedded (FFPE) block specimens.
- 9. Female subjects of childbearing potential have a negative urine or serum pregnancy test within 7 days prior to enrollment. If the urine test is positive or cannot be confirmed as negative, a serum pregnancy test will be required. It is allowed that the test at the same day at 7 days prior to enrollment. And male / female subjects of childbearing potential must agree to use an adequate method of contraception starting with signing the informed consent through 120 days after the last dose of study medication.
- 10. Demonstrated adequate organ function as defined in following criteria. All screening labs should be performed within 14 days of enrollment. Note: Subject must not have taken transfusion, hematopoietic agent; granulocyte-colony stimulating factor (G-CSF) etc., and/or oxygen supplementation within 7 days before the screening labs.
- a. Absolute neutrophil count (ANC)  $\geq$  1,000 /mm3
- b. Platelets  $\geq 100,000 / \text{mm3}$
- c. Hemoglobin  $\geq 8.0 \text{ g/dL}$
- d. Serum total bilirubin  $\leq 2.0 \text{ mg/dL}$
- e. Aspartate aminotransferase (AST) (SGOT) and alanine aminotransferase (ALT) (SGPT) $\leq 3x$  Upper limit of normal (ULN). For subjects with liver metastases  $\leq 5x$  ULN.
- f. Serum creatinine $\leq 2.0 \text{ mg/dL}$ ; or if serum creatinine > 2.0 mg/dL, measured or calculated creatinine/clearance  $\geq$ 45 mL/min (Cockcroft-Gault formula).
- 11. Life expectancy of  $\geq 4$  months from the first OBP-301 treatment.

12. Understand the study requirements and the treatment procedures, and is willing to comply with all specified follow-up evaluations, and provides written informed consent before any study-specific tests or procedures are performed.

# 4.3 Exclusion Criteria

The presence of any of the following criteria will constitute cause for the exclusion of the participant:

- 1. Is currently participating and receiving study therapy or has participated in a study of an investigational agent and received study therapy within 4 weeks of study Day 1.
- 2. Has an active autoimmune disease that has required systemic treatment in past 2 years.
- 3. Has a diagnosis of immunodeficiency or is receiving systemic steroid therapy (greater than equivalent of 20 mg/day) or any other form of immunosuppressive therapy within 7 days prior to study Day 1.
- 4. Has known active central nervous system metastases and/or carcinomatous meningitis.
- 5. Has had prior anti-cancer monoclonal antibody chemotherapy, targeted small molecule therapy, or radiation therapy within 2 weeks prior to study Day 1, who has not recovered from adverse events due to a previously administered agent.
- 6. Has a known additional malignancy within 3 years before the first OBP-301 administration that is progressing or requires active treatment, with the exception of prostate cancer controlled with androgen deprivation therapy.
- 7. Has received a live vaccine within 30 days of planned start of study therapy.
- 8. Patients known to have acute or chronic active hepatitis B virus (HBV), hepatitis C virus (HCV) or human immunodeficiency virus (HIV).
- 9. Has any evidence of active, non-infectious pneumonitis or interstitial lung disease requiring steroids.
- 10. Has an active infection requiring systemic therapy within 2 weeks of Day 1.
- 11. Has known psychiatric or substance abuse disorders that would interfere with cooperation with the requirements of the trial.
- 12. Is pregnant or breastfeeding, or expecting to conceive or father children within the projected duration of the trial, starting with the screening visit through 120 days after the last dose of trial treatment.
- 13. Previous severe hypersensitivity to another monoclonal antibody
- 14. Has a history or current evidence of any condition, therapy, or laboratory abnormality that might confound the results of the trial, interfere with the subject's participation for the full duration of the trial, or is not in the best interest of the subject to participate, in the opinion of the treating investigator.
- 15. Uncontrolled intercurrent illness including, but not limited to, uncontrolled diabetes, ongoing or active infection, symptomatic congestive heart failure, unstable angina pectoris, cardiac arrhythmia, or psychiatric illness/psychological incompetence, whereby in the opinion of the Investigator the patient is assessed as being unable to provide information, consent, or comply with the study requirements and procedures.
- 16. Patients who are pregnant or breastfeeding, or expecting to conceive or father children within the projected timeframe of the study, starting from the time of the Screening Visit through 4 months (120 days) after the last OBP-301 administration. Females of childbearing potential must have a negative serum or urine pregnancy test at screening. A female not of childbearing

Page 31 V8.0 potential is one who has undergone bilateral oophorectomy or who has had no menses for 12 consecutive months.

Page 32 V8.0

### 4.4 Registration Procedures

### 4.4.1 Patient Registration – Part 1 (WCMC Only)

Patients will be centrally registered with the Office of Billing Compliance. To register a patient, submit the following documents via the JIRA Registration Process:

- Legible copy of the HRBAF
- First and last page of signed informed consent form
- Registration must be completed within 24 hours of the signing of informed consent.

#### 4.4.2 Patient Registration – Part 2 (All Sites)

Study participants will be centrally registered Monday through Friday from 9:00am to 4:00pm with the Weill Cornell Medicine Joint Clinical Trials Office (JCTO). To register a new study subject, email the following documents to [contact]:

- Completed WCM subject registration form
- First and last page of the fully executed informed consent form, plus additional pages if checkboxes for correlative studies are required
- Fully executed HIPAA research authorization form
- Eligibility checklist signed and dated by investigator and research nurse
- Documentation of any eligibility waivers granted
- Redacted source documentation to verify eligibility

Note that attachments larger than 4.5 MB are not accepted, so larger attachments should be split into more than one email. Central registration information is reviewed and entered into the REDCap database.

#### 4.5 Stopping Criteria

#### 4.5.1 Patient Withdrawal Criteria

In accordance with applicable regulations, a participant has the right to withdraw from the study, at any time and for any reason, without prejudice to his future medical care.

Withdrawal from the study and therapeutic measures taken shall be at the discretion of the Investigator. A full explanation for the discontinuation from the study should be made in the participant's medical records and in the eCRF.

Premature discontinuation from active study participation may occur at any time due to any of the following reasons:

- Any situation where, in the opinion of the Investigator or the Medical Monitor, continued participation in the study would not be in the best interest of the patient.
- Positive pregnancy test (see Section for procedures to be followed in case of a pregnancy).
- Patient initiates other anti-cancer therapy. The anti-cancer therapy will be documented in the medical record and eCRF.
- Patient is unable or unwilling to comply with study procedures.
- Patient is lost to follow-up.
- Patient withdraws consent.
- Request by a Health Authority.
- Termination of the study by the study investigator(s).
- Progressive neoplastic disease, unless the Investigator feels this may be pseudoprogression, in which case the patient may remain on study until the next evaluation for extent of disease.

The reason(s) for premature study discontinuation/withdrawal should be reported in the eCRF and within the source documents along with the date of withdrawal. AEs should be documented according to Section 7.0 Adverse Events.

For all patients who discontinue, a Final Visit will be performed within  $28 \pm 5$  days after the last IP administration. If a participant is withdrawn because of an AE, the Investigator must arrange for the participant to have appropriate follow-up care until the AE is resolved or has stabilized. Unresolved AEs will be followed until the last scheduled follow-up visit or until the Investigator determines that further follow-up is no longer indicated. Investigators should attempt to collect the survival information as dictated in section 6.1.3.

Patients who discontinue the active study participation will not be replaced.

Any enrolled patients who are discontinued before study dosing will be documented as screen failures in the eCRF and replaced. No follow-up is required for these patients.

### 4.5.2 Termination or Suspension of the Study

Investigator and the IEC/IRB reserve the right to terminate or suspend the study at any time for medical, safety, regulatory, administrative, or other reasons consistent with applicable laws, regulations, and Good Clinical Practice (GCP); however, this should be discussed between the relevant parties beforehand and the reason for such decision recorded. Should this occur, all data available will also be recorded in the eCRFs. The Investigator should notify the IEC/IRB in writing of the study's completion or early discontinuation.

We have included adverse events stopping rule (see Section 8.7.9).

In the event that the study is terminated early, the Investigator should make every effort to follow AEs and SAEs for all patients until the end of the defined follow-up period resolution, until the condition stabilizes, until the event is in the opinion of the Investigator stabilized or determined to be chronic, or until the participant dies or is lost to follow-up. SAEs that occur after the Final Visit, that are thought to be related to the administration of OBP-301, should be reported to Oncolys BioPharma Inc. or designee.

Page 33 V8.0

### 5 STUDY MEDICATION

#### 5.1 Investigational Product (IP) Identification

The OBP-301 clinical study material and product is generated according to current Good Manufacturing Practice (cGMP). Table 1 shows an overview of OBP-301. OBP-301 will be provided by Oncolys BioPharma Inc.

Table 1	Investigational Product Information
---------	-------------------------------------

Investigational product code:	OBP-301
Content:	$2 \text{ mL/vial} (1 \times 10^{12} \text{ VP/mL})$
Dosage form:	Solution; formulated in 20 mM Tris pH 8.0, 25 mM NaCl with 2.5% glycerin, USP by volume, filled in each 5 mL glass vial
Storage method for the investigational product:	Store at $\leq$ -60°C

### 5.2 Dosage and Treatment

1. OBP-301  $2x10^{12}$  viral particles/ tumor injection every 2 weeks x 4 injection encounters.

\* Up to 1 additional tumor injection encounter may be considered in discussion with the PI ([name]) which may be given 2 weeks after the 4th injection of OBP-301.

\* OBP-301 will be administered as a fixed dose to the tumor. The target dose of OBP-301 injection will be  $2x10^{12}$  VP (i.e. 1 vial), and a minimum of  $1x10^{12}$  VP (i.e. 1 ml). Specifically, inject as much OBP-301 as possible, but within 1 - 2 mL. The maximal injection volume of 2.0 mL is preferred (2  $x10^{12}$  VP per lesion) and should be injected as long as this is technically possible. At least 1 mL OBP-301 should be injected to the same location as the 1st and 2nd injection even though the primary tumor mass may have decreased and may be hard to locate.

\* OBP-301 will be administered to one lesion. If the gastroesophageal tumor is multifocal, only the largest lesion will be targeted.

\* For patients with tumors not assessable by endoscopy, injection via interventional radiology procedure is permitted, applying the same dosing principles above.

\* Note that it is expected that some amount of material will be used to prime the injection device (i.e. 0.8 mL for a Carre-Locke injection needle). This will be discarded as per standard procedure.

2. Pembrolizumab 200mg intravenous every 3 weeks until disease progression.

Page 35 V8.0

Please note that the Pharmacy manual, which is used for all OBP-301 studies globally, also indicates another OBP-301 dose administration option (plan B). This protocol will only use Plan A (i.e. fixed dose administration).

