# 5.2.1.2 Accountability and Compliance

The Investigator, pharmacist, or designee, may only dispense clinical supplies in accordance with this protocol.

The Investigator, pharmacist, or designee, is responsible for maintaining an accurate and current record of all clinical supplies received from Oncolys BioPharma Inc., dispensed to the Investigator or destroyed. Accountability records must be maintained throughout the course of the study, showing receipt and disposition of the clinical supplies.

At the end of the study, it must be possible to reconcile delivery records with that of used, unused and destroyed clinical supplies.

The Investigator is also responsible for the education of study staff in the correct administration of the IP.

Additional measures to ensure treatment compliance are not required because the IP will be prepared and administered by study personnel (see Section 5.2.1.3).

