# 5.2.3 Injection Procedures

The optimum technique for injection of a primary tumor is to inject the viral particles circumferentailly around the lesion in 4 quadrants, similar to the technique used in endoscopic submucosal disection (Gotoda T, et al. J Gastroenterol 2006;41:929-942.). This will ensure that the viral partical will be maximally penetrated into the lesion.

Endoscopists who perform single polypectomies will be eligible to perform the procedure. A trianing video (prepared by Oncolys Biopharma) is available as well.

The procedure will be performed in the Endoscopy Unit or interventional suite with standard sterilization procedures. A standard gastroscope and needle (eg. GIF-HQ190 Olympus gastroscope with 25 gauge Carr-Locke injection needel made by US Endoscopy) is used for the procedure. Guidelines for each injection procedure are provided below.

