# 8.4.4 Per-Protocol (PP) Population

Per-Protocol population will only include individuals who completed all four doses of OBP-301 and followed the study protocol

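### One 2 mL vial less the stated 0.8 mL priming loss leaves 1.2 mL, so the one-vial target and the preferred 2.0 mL injection do not fit together for the named needle, and delivered dose may vary unseen

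*Combined protocol and SAP*

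**What the plan says.** - **Vial (Section 5.1, Table 1).** 2 mL per vial at 1 × 10^12 VP/mL. Section 5.2.2 repeats the content as 2 × 10^12 VP per vial.
- **Target, minimum and range (Section 5.2).** The target is 2 × 10^12 "VP (i.e. 1 vial), and a minimum of" 1 × 10^12 "VP (i.e. 1 ml). Specifically, inject as much OBP-301 as possible, but within 1 - 2 mL". Also: "The maximal injection volume of 2.0 mL is preferred", on condition that the technique allows it.
- **Priming (Section 5.2).** It is expected that "some amount of material will be used to prime the injection device (i.e. 0.8 mL for a Carre-Locke injection needle"), and this volume is discarded.
- **Device and route.** Sections 3.1 and 5.2.3 make endoscopic injection of the primary tumor the main route. The only needle named for it, as an example, is a "25 gauge Carr-Locke injection needel made by US Endoscopy". Section 5.2 also permits injection by interventional radiology under the same dosing approach, but gives no priming loss for that route.
- **Compliance and accountability (Sections 5.2.1.2 and 5.2.1.4).** "Additional measures to ensure treatment compliance are not required because the IP will be prepared and administered by study personnel". Supplies are reconciled and vials are accounted for on a form. Part-used vials are foreseen and destroyed.
- **Per-protocol set (Section 8.4.4).** "Per-Protocol population will only include individuals who completed all four doses of OBP-301" and who also followed the protocol. No delivered volume is named.

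**The concern.** Section 5.2 treats three things as holding together: one vial, 2.0 mL into the tumor, and 0.8 mL lost to priming. With a 2 mL vial and the named needle they cannot all hold. This is not an occasional difficult injection, because the protocol itself expects the loss. A team that takes the one-vial figure at face value and uses that needle will fall short of the target every time.

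The Synopsis and Section 6.1.2 say that all patients receive 2 × 10^12 VP per injection, and both primary objectives (response rate and safety) will be read as results for that dose. One site may open a single vial and another may open two, and each could fairly claim to follow Section 5.2. The planned analyses would not separate them: Section 8.7 has no summary of OBP-301 exposure or injected volume, and Section 8.3.1 says only that REDCap captures treatment data, without listing fields.

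**Working it through.** **Inputs**
- Vial volume 2.0 mL, concentration 1 × 10^12 VP/mL (Section 5.1, Table 1)
- Target 2 × 10^12 VP, minimum 1 × 10^12 VP, injected volume 1–2 mL with 2.0 mL preferred (Section 5.2)
- Priming loss 0.8 mL for the named needle, discarded (Section 5.2)
- Four planned injections (Section 5.2)

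**Step 1. Reproduce the plan's figure.** Vial content = volume × concentration = 2.0 × 1 × 10^12 = 2 × 10^12 VP. This equals the target exactly, but only before any priming loss.

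**Step 2. Deliverable from one vial.** (2.0 − 0.8) mL = 1.2 mL; 1.2 × 1 × 10^12 = 1.2 × 10^12 VP.
- Share of target: 1.2 / 2.0 = 60%
- Ratio to the stated minimum: 1.2 / 1.0 = 120%

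**Step 3. Volume needed to inject a given amount.**
- For 2.0 mL: 2.0 + 0.8 = 2.8 mL = 1.4 vials, so two vials must be opened
- For the 1 mL minimum: 1.0 + 0.8 = 1.8 mL = 0.9 vial
- From two vials: 4.0 − 0.8 = 3.2 mL, enough for 2.0 mL
- From one vial alone, 2.0 mL would need 2.8 mL of usable fill, which is 40% above the stated 2 mL

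**Step 4. Over the course.** Four injections: 4 × 1.2 = 4.8 against 4 × 2.0 = 8.0 (× 10^12 VP).

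**Step 5. Spread between practices.** Two vials against one: 2.0 / 1.2 = 1.67. If vial content were recorded when 1.2 × 10^12 VP was delivered, the record would be 2.0 / 1.2 − 1 = 67% too high. The documents state no such recording rule, so this is conditional.

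**Step 6. Sensitivity to priming loss, one vial.** Only 0.8 mL comes from the documents; the other losses are assumptions.

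| Priming loss (mL) | Injected (mL) | Share of target |
|---|---|---|
| 0 | 2.0 | 100% |
| 0.4 | 1.6 | 80% |
| 0.8 | 1.2 | 60% |
| 1.0 | 1.0 | 50% (the stated minimum) |

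**Step 7. Design.** None of these quantities enters the two-stage calculation. As a side check, the rule in Section 8.8 (18 then 37 patients; at least 3 then at least 9 responders) gives an exact alpha of 0.087 and power of 0.806, in line with the stated 10% and 80%.

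**The case against.** The strongest reply is that Section 5.2 is not breached. It sets a range, and 1.2 mL lies inside it and above the minimum; 2.0 mL is a preference that depends on technique. The reference to one vial sits beside a matching reference to 1 mL, and both can be read as equivalents of a quantity rather than limits on dispensing. Nothing forbids a second vial, and two vials supply the 2.0 mL. Section 5.2.1.4 leaves preparation detail to a Pharmacy Brochure that is not among the documents and may settle the vial count. Vial accountability would show where a second vial was opened. Section 5.2 already speaks of volume injected, and the per-protocol definition requires adherence to the protocol as well as four doses.

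Most of this stands, and it limits the point. A reader might infer that the target cannot be delivered endoscopically at all, that the recorded dose is overstated, or that most endoscopically treated patients receive 60% of the target. The documents support none of these. The first needs a one-vial limit that is not stated. The second needs a recording rule that is not stated. The third needs device and vial usage that is not given, and the needle is only an example.

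The reply does not remove the mismatch. The only vial count in Section 5.2 is one, and with the stated loss it misses the stated target. A range that admits both 1.2 and 2.0 mL explains how practice can diverge; it does not show which was given. Vial counts do not give the volume injected. A manual outside the protocol does not cure a conflict within it, and Section 5.2 itself warns that the global manual contains a dosing option that this trial does not use.

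**Conclusion.** The point holds in a limited form. On the protocol's own figures, the one-vial target and the preferred 2.0 mL injection cannot both be met from a single vial with the named needle: at most 1.2 mL (1.2 × 10^12 VP) can be delivered, 40% below target and 20% above the minimum. Whether patients receive 1.2 or 2.0 × 10^12 VP, or something between, depends on vials opened, device and route, none of which the protocol fixes. Overstatement of the reported dose is possible, not shown.

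The figures assume nominal vial fill, a 0.8 mL loss at each encounter, and no flushing of the primed volume into the tumor. The documents are silent on overfill and flushing. The consequence lies in the dose to which the primary efficacy and safety results are attributed, not in the sample size or the decision rule.

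**What to change.** 1. **Reconcile Sections 5.1 and 5.2.** State the number of vials prepared per encounter, the priming loss for each device and route in use, and whether the dose figure means volume withdrawn or volume injected. Which dose is intended is for the sponsor to decide. Two other passages should be brought into line at the same time: Section 3.1, which gives 1 × 10^12 VP per injection, and Section 5.2.2, which lets lesion diameter set the volume despite the fixed dose in Section 5.2.
2. **Record delivery.** For each injection, the eCRF should hold volume drawn, volume primed or discarded, volume injected, and route.
3. **Report delivery.** Give delivered VP by patient and route alongside the efficacy and safety results.

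The cost is protocol and pharmacy wording, a few eCRF fields and one additional summary. Depending on how the sponsor reconciles the passages, more product per encounter might be needed. The reported dose may turn out less favourable than the nominal one.

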# 5.2.1 Study Supplies

Pembrolizumab will be supplied by commercial venders.

Oncolys BioPharma Inc. will be responsible for the preparation and labelling of the Investigational Product in accordance with local regulatory requirements. Oncolys BioPharma Inc. will also provide details of batch numbers and all associated safety and stability data.

Oncolys BioPharma Inc. will be responsible for packaging and shipment of the IP to the site(s). Due to product specific requirements, shipments of IP will be made on dry ice using a validated container and temperature monitoring. An official shipping form to be completed by the study Investigator or designee (e.g., pharmacist) will be included in each shipment. Specific ordering information will be provided to each participating site upon study activation.

